An estimated 40 000 children are newly infected per annum in South Africa and the current mother-to-child transmission (MTCT) rate is 4% at 4-8 weeks despite the 88% ARV prophylaxis coverage [14]. Despite the encouraging reports of lower incidence of paediatric HIV infections as a result of PMTCT programmes, a study by Johnson et al modelled a 34% projected increase in MTCT from recently infected mothers in the absence of any intervention [15]. The study further cautions that MTCT from women who seroconvert during lactation will become the dominant mode of MTCT. In the KZN seroconversion cohort study, the group of HIV-exposed children was 2.3 times at higher risk of infection (MTCT 20.5% [8/9] vs 9.0% (83/925]) [5].

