To explore the safety of Truvada when used as PrEP in combination with current recommendations for prevention of sexually transmitted infections and HIV in young women at substantial risk of HIV acquisition during pregnancy and lactation.

2.2 Primary Objective:

 To compare the frequency and seriousness of specific adverse events related to TDF/FTC in women and their children in Arm A (exposure to TDF/FTC) and Arm B (no exposure to TDF/FTC) during pregnancy until breastfeeding cessation.

2.3 Secondary Objectives:

- To estimate HIV incidence in women in ARM A with ARM B at delivery and at 18 months post-delivery.
- To determine the interdependency of adherence to a once daily oral TDF/FTC regimen and standard HIV prevention methods during pregnancy and postdelivery.
- To measure antiretroviral drug (TDF/FTC) level in women and their infants in association with adherence, safety and level of protection (plasma and breastmilk)
- To detect drug resistance among women who acquire HIV infection and correlate the treatment outcomes (after initiating immediate ARV treatment) with drug resistance
- To determine mother-to-child transmission of HIV among women who acquire incident infections during pregnancy and breastfeeding and the frequency of drug resistance in their infected babies

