7.13 Followup Visits for Infants

Infants will be assessed at birth, 26 weeks, 50 weeks and 74 weeks. In addition to a full physical examination, a blood sample will be drawn for assessing renal function (Creatinine Clearance) and Hormonal growth factors. For infants exposed to TDF/FTC an additional blood sample will be collected for a drug level assessment. At each visit the following growth parameters will be recorded: weight, height and head circumference. Infant feeding modality will be recorded at each visit. Cessation of breastfeeding is defined as 28 days after last exposure to breastmilk.

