When a participant tests HIV positive on the first sample according to the study algorithm, she will be counselled and asked to immediately provide a second sample (10ml in EDTA tube) for a repeat of the HIV algorithm tests as confirmation of the first positive result. According to site SOPs the following samples will also be taken either immediately after the first sample is positive or after the second sample has confirmed the first positive result:

• 10ml in EDTA tube for HIV PCR, HIV-1 viral load and resistance testing;

and,

• 2ml in BD CD4 stabilization tube or 3ml in EDTA tube for CD4 count;

A plasma aliquot will be stored (long term storage) if sufficient sample is available for potential future HIV related research (if participant consented). If the visit of the HIV diagnosis does not coincide with a visit in which secondary endpoints are assessed, another 5-10ml blood in serum tubes (dependent on the site, see site specific lab SOPs) will be collected and tested for AST, ALT, phosphorus and creatinine; a serum aliquot will be stored (long term storage) for potential future HIV related research (if participant consented). HepBsAg testing will be done if appropriate. Procedures for early product withdrawal will also be done.

Samples from her previous visit(s) will be tested by HIV PCR to better determine the infection time and length of exposure to Truvada while HIV infected. Samples from visits in which she was HIV PCR positive but HIV antibody negative will also be tested for resistance and drug levels. At her first follow-up visit after the diagnosis (week 4 post diagnosis), HIV testing according to the study algorithm will be repeated. HIV testing will stop if the first algorithm testing gives a positive result. At each monthly visit post HIV diagnosis, study staff will:

- Update contact information (when necessary);
- Update her medical history, including her medication;
- Conduct further risk reduction counselling and distribute free condoms

7.15 Followup Visits for Children Born to Women who Seroconvert During Pregnancy or Breastfeeding

All HIV exposed infants will continue with study followup until 18 months of age.

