Infants born to women who seroconvert during pregnancy will have a HIV DNA PCR test performed at birth and 3 monthly thereafter until cessation of breastfeeding. These infants will also receive antiretroviral prophylaxis (according to the National PMTCT Guidelines) commencing at birth until breastfeeding cessation.

Infants being breastfed by a mother who seroconverts during breastfeeding will have a HIV DNA PCR test performed at the visit when the mother's HIV status is confirmed and 3

monthly thereafter until cessation of breastfeeding. The infant will commence antiretroviral prophylaxis according to the National PMTCT Guidelines.

Infants with confirmed HIV infection (Positive HIV DNA PCR on 2 separate specimens) will be managed according to the National Treatment Guidelines and in addition to routine haematological and chemistry tests al blood sample will be drawn for resistance testing.

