10.2 Outcome Measures

Main Outcome Measure:

 Renal Function estimated by Serum Creatinine Clearance, adverse pregnancy outcomes (e.g., stillbirth, preterm delivery at < 37 weeks gestation, low birth weight <2,500 grams, and congenital anomalies) and Bone Mineral Density among women

Bone Mineral Density and growth parameters in neonates and infants until cessation of breastfeeding.

Other Outcome Measures:

- Confirmed presence of HIV infection detected by HIV NAT positivity at scheduled 3 monthly visits until 18 months.
- Adherence -self reported use of study product and pill count
- Partners HIV status at enrollment confirmed by Two POC tests and Adherence measured at delivery and 18 months postdelivery
- Antiretroviral drug level in plasma as a marker of adherence.
- Presence of viral resistance mutations that have been selected by Truvada (K65R, M184V) in participants who acquire HIV infection
- Mother to child transmission-reactive NAT testing performed in children born to mothers who acquire HIV infection during pregnancy and post-delivery.

Behavioural Risk:

- Number of sexual partners with whom participant had unprotected intercourse during pregnancy and postnatally
- Number of protected and unprotected acts of intercourse during pregnancy and postnatally
- Sexually transmitted infections acquired during pregnancy
- Sexually transmitted infections acquired postnatally
- Facilitators and barriers to adherence.

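### Scheduled HIV testing of infants of seroconverting mothers ends at breastfeeding cessation, with no test tied to or after it and no final time point, so the mother-to-child transmission estimate can be biased low

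*Combined protocol and SAP*

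**What the plan says.** One secondary objective (section 2.3) is "To determine mother-to-child transmission of HIV among women who acquire incident infections during pregnancy and breastfeeding", together with the frequency of drug resistance in the infected babies. Section 10.2 defines the outcome as "Mother to child transmission-reactive NAT testing performed in children born to mothers who acquire HIV infection during pregnancy and post-delivery". It gives no age or visit at which the child's status becomes final.

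The only infant PCR rule is in section 7.15. Infants of women who seroconvert in pregnancy "will have a HIV DNA PCR test performed at birth and 3 monthly thereafter until cessation of breastfeeding". Infants of women who seroconvert while breastfeeding are tested at the visit that confirms the mother's status, then every 3 months to the same end point. A confirmed infant infection needs two positive PCRs on separate specimens.

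Two other statements matter. Section 7.13 says "Cessation of breastfeeding is defined as 28 days after last exposure to breastmilk", so the testing window runs 28 days past the last exposure. Section 7.15 also says "All HIV exposed infants will continue with study followup until 18 months of age", so these children remain under observation after their scheduled PCRs have ended. Appendix 6 lists stored infant dried blood spots (DBS) through to the exit visit, but it is headed for HIV-unexposed infants and has no PCR row.

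**The concern.** Breast milk exposure continues until weaning, and infection acquired near its end can be seen only by a test taken after it. The rule closes the testing window 28 days after the last exposure and does not require a test inside those 28 days. With 3-monthly spacing, whether one falls there is a matter of timing.

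Two groups fare worse. A never-breastfed infant of a woman infected in pregnancy has, as worded, the birth PCR only. An infant weaned on the day of the mother's diagnosis is tested that day, and the window closes before the next test is due.

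At stake are the transmission proportion and the number of infected babies available for resistance testing. Expected numbers are small, so one to three missed infections could change the estimate noticeably.

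**Working it through.** **Inputs.** Testing every 3 months, taken as 91 days (7.15); window closes 28 days after last exposure (7.13); 66 maternal infections (10.3, secondary endpoint). Assumptions, because the documents give no figure: timing of the last test relative to weaning (uniform), PCR detection lag *w*, months of breastfeeding remaining after maternal infection, constant transmission hazard, and the transmission rate.

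**The plan's own figures.** Schoenfeld's formula for a hazard ratio of 0.5, two-sided 5%, 80% power: 4 × (1.96 + 0.842)² / (ln 0.5)² = 65.4, so 66 events, as stated. Two proportions, 12.72% against 6.36%, two-sided, no continuity correction: 334 per group, as stated. The plan gives no figure for infant transmission itself.

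**Infants with no test after last exposure.** A test falls within the 28-day window with probability 28/91 = 31%, leaving 69% without one. With 84-day spacing, 28/84 = 33% and 67%.

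**Exposure not covered by a test.** Let *u* be the days from the last test to the end of the window, uniform on 0 to 91. Uncovered exposure is max(0, *u* − 28 + *w*) days.
- *w* = 0: mean (91 − 28)² / (2 × 91) = 3969/182 = 21.8 days, maximum 63.
- *w* = 14: mean 77²/182 = 32.6 days, maximum 77.
- *w* = 28: mean 91/2 = 45.5 days, maximum 91.

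**Share of postnatal transmissions missed** (mean uncovered days divided by remaining breastfeeding days):

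| Breastfeeding remaining | *w* = 0 | *w* = 28 days |
|---|---|---|
| 3 months (91 d) | 21.8/91 = 24% | 45.5/91 = 50% |
| 6 months (182 d) | 12% | 25% |
| 12 months (365 d) | 6% | 12.5% |

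**If a test at cessation is intended.** That test falls 28 days after last exposure, so uncovered exposure is max(0, *w* − 28): zero for lags up to 28 days, and 14 days for a 42-day lag.

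**Two cases that do not depend on random timing.**
- Weaned at the mother's diagnosis: test on day 0, window closes on day 28, next test due about day 91. Since 28 < 91, the day-0 test is the only one.
- Never breastfed, mother infected in pregnancy: birth test only. There is no last breast milk exposure, so no cessation date exists to trigger another.

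**Scale.** At an assumed 10% transmission, 66 × 0.10 = 6.6 infant infections; at the 20.5% printed in section 1.5, 66 × 0.205 = 13.5. Taking 13.5, a missed share of 6–24% is 0.8–3.2 infants, and 12.5–50% is 1.7–6.8. These are upper guides: they treat every transmission as postnatal, and maternal infections after weaning expose no infant. Section 1.5 also prints 20.5% beside the fraction 8/9, which is 89%, so that rate serves only for scale.

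**The case against.** The best defence is that *until cessation* includes a test at cessation. On that reading the loss is about zero for breastfed infants at lags up to 28 days. The text neither says nor excludes this. It would not help the never-breastfed infant, who has no cessation date.

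A second defence is that children stay in follow-up and specimens are stored. Section 7.16 does permit repeat and confirmatory analyses. But it describes sera or plasma, only says they may be used, and has study samples destroyed after the final report. Late detection is possible but not planned.

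A reader might infer several stronger things that the documents do not support:
- *That 69% of transmissions are missed.* The 69% counts infants without a test after last exposure. Infections acquired earlier are still found by the earlier tests.
- *That every transmission in the last interval goes uncounted.* The 28-day definition already carries testing past exposure for some infants.
- *That untested children are classed as uninfected.* The plan does not say how they are classified. If they were dropped as unevaluable, the denominator would shrink instead.
- *That the background shows what a birth test misses.* Section 1.5 says "the current mother-to-child transmission (MTCT) rate is 4% at 4-8 weeks"; it does not separate infections already detectable at birth.
- *That early weaning or never breastfeeding is common here.* No frequency is given, and section 1.11 expects most HIV-infected women in the region's public sector to breastfeed.
- *That 66 is a forecast of exposed infants.* It is the number of maternal infections needed for power. The 20.5% is likewise not a forecast, since section 6.11 puts mothers who seroconvert on treatment and section 7.15 gives their infants prophylaxis, neither of which is modelled here.

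**Conclusion.** The gap is real but limited. As written, scheduled infant PCR ends at breastfeeding cessation, no test is tied to or follows it, and the outcome has no final ascertainment time. Late or peripartum transmissions can therefore be missed. Where children with a missed infection are counted as negative, the transmission proportion and the count of infected babies for resistance are biased low.

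If no test at cessation is intended, the missed share of postnatal transmissions is roughly 6–24% with instant detection and 12.5–50% with a 28-day lag, on the assumptions of random test timing, constant hazard and 12 down to 3 months of remaining breastfeeding. If such a test is intended, the loss is near zero for breastfed infants at lags up to 28 days, and the never-breastfed case remains.

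The objective is secondary and descriptive, and the primary safety comparison is untouched. The change is still worth making because it is cheap and the expected number of infant infections is small.

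**What to change.** For outcome ascertainment only:
- In sections 7.15 and 10.2, define the outcome as cumulative mother-to-child transmission to 18 months.
- Run a NAT on the infant sample already drawn at the exit visit (7.13) for every child whose mother seroconverted in pregnancy or breastfeeding, whatever the feeding status.
- State that the DBS storage in Appendix 6 also covers HIV-exposed infants. If the exit visit is missed, use the last stored DBS taken after cessation.
- Confirm a reactive exit result on a second specimen, in line with the two-specimen definition in 7.15.
- Report separately any child still breastfeeding at exit, whose exposure is not over.
- Say how children without a final test enter the numerator and denominator.

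Sections 7.13, 7.15 and 10.2 and Appendix 6 should be reconciled, including whether *until cessation* includes a test at that point and whether the infant exit visit is week 74 (7.13) or week 72 (7.21, Appendix 6).

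Cost: on the plan's 66 maternal infections, at most about 66 extra assays on blood from a visit already planned, plus confirmations, some of which need a further specimen after exit, and a few sentences of text. Clinical testing and prophylaxis stay with the national guidelines the protocol cites.

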7.16 Stored Specimens

Any blood specimens (i.e. sera or plasma) collected during screening, enrollment, and all follow-up visits will be cryopreserved during the clinical trial and stored at the Global Clinical Lab repository. These specimens may be used for repeat and confirmatory analyses of effectiveness, safety endpoint parameters, and drug levels. These study samples will be destroyed after the final study report has been submitted. At enrollment, participants will be asked to sign a specimen storage informed consent form for long term storage of samples (ten years after final study report) for any future testing related to HIV research that falls outside of this study. These additional specimens will be stored for a period of 10 years and thereafter destroyed.

7.17 Participant Retention

The target retention rate will be 90% per annum. During the informed consent process the participant will be informed of the planned retention procedures. This is to ensure participant awareness of all the efforts that will be undertaken to contact them in the event that they miss a scheduled study visit throughout the participant's Involvement in the study (up to 2 years for those who enroll early in pregnancy). Study participants will be informed that staff will attempt to make telephonic contact with them for missed visits or for unscheduled visits if the need arises, failing which home visits will be made. The Protocol Team will track retention rates. Once a participant is enrolled in the study, study staff will make every reasonable effort to ensure adequate locator information is available for follow-up tracking. A missed visit in either arm will prompt a single telephonic reminder, where the participant is spoken to directly and reminded of her clinic visit. A home visit will be triggered if a second clinic visit is missed. A home visit will be considered complete when the participant is met in person. A maximum of 3 attempts will be made to complete a home visit. Retention efforts will be conducted by the same team for both arms.

7.18 Participant withdrawal

Participants may voluntarily withdraw from the study for any reason at any time. Designated study staff may also withdraw participants from the study in order to protect their safety. Participants may also be withdrawn if the South African MCC or the University of KwaZulu-Natal's (UKZN) Biomedical Research Ethics Committee (BREC) terminates the study prior to its planned end date. Every reasonable effort will be made to complete a final evaluation of participants who withdraw or are withdrawn from the study. Study staff will record the reason(s) for all withdrawals in participants' study records.

7.19 Sexual Partners

Sexual partners of study participants will be invited to attend the HCT services but not participate in the study. They will have access to HIV counselling and testing,

appropriate clinical referrals for HIV treatment, STI management and other medical conditions. Study staff will not obtain informed consent from any men, nor will they enroll or collect data from them. Whenever a participant tests positive for any STI (excluding HIV), she will be counselled to inform her partner(s) and refer him/them to a clinic for testing. Treatment for any curable STI will be offered to the male partner if he comes to the study clinic. Local guidelines on partner notification will be followed. Participants will decide on disclosing their HIV status to their partners and study staff will support her decision.

7.20 Procedures for Assessing HIV Seroconversion

Women will have a rapid HIV test performed at every visit using the serial testing algorithm as per national guidelines. In the event of a reactive rapid HIV test, a repeat sample will be obtained and reactivity confirmed by HIV RNA PCR assay. In the event of a confirmed seroconversion, a genotypic drug resistance test will be performed to identify mutations as a result of exposure to Truvada.

7.21 Procedures for Assessing Safety

Participants will be asked one month after starting Truvada and at each subsequent scheduled visit whether they have had any admissions to hospital, or suffered from any significant illness that required medical attention. The site clinician will determine whether an illness meets the criteria for Serious Adverse Event (SAE) Reporting. SAEs will be reported to the UKZN BREC, Medicines Control Council and Department of Health. Participants will also be asked whether they have experienced any side effects.

Clinical assessments during pregnancy will be conducted as per the national guidelines for maternity care.

Maternal safety assessments during pregnancy and until 74 weeks study exit: All women will have bloods drawn for chemistry and haematological investigations at screening, enrolment, 2 weeks, 4 weekly until delivery, <72 hours of delivery, 2 weeks post delivery, 6 weeks, 10 weeks, 14 weeks and 4 weekly until 74 weeks (inclusive). Chemistry tests include liver function markers (ALT/AST/Phosporous), renal function (serum creatinine/urea/sodium/potassium), and bone density markers (serum calcium and magnesium).

Bone mineral content in the mother will be measured by DXA scan at 6 weeks postpartum, 6 months, 12 months and 18 months. Both Hip and Spine DXA scans will be done at above scheduled visits.

Within 72 hours of delivery, the participant with her maternity care record (MCR) will be reviewed by the study clinician. Fetal outcome in addition to other obstetric data will be extracted from the MCR. The following definitions will be used to document fetal outcome:

NON-VIABLE FETUS (MISCARRIAGE)

Less than 28 weeks* gestation and where there is no evidence of life at delivery. **STILL BIRTH** Gestational age of 28 weeks or more and where there is no evidence of life at delivery. **NEONATAL DEATH**** Death after a live birth whatever the duration of the pregnancy. **When the gestational age is not known, a legal weight cut-off of 1000 g is used.**

Maternal gestational age will be determined by clinical and obstetric assessments that will include an Ultrasound, measurement of symphysis fundal height and last menstrual date if known. Preterm delivery is defined as < 37 weeks. Moderate preterm delivery 32-35 weeks and severe preterm delivery <32 weeks.

The New Ballard method will be used to assess gestational age of neonate. In addition, neonates will be determined small for gestational age (SGA), average for gestational age (AGA) and large for gestational age (LGA).

Fetal Growth:

Fetal monitoring will include fetal growth and an ultrasound for fetal abnormalities. For fetal growth monitoring, we would measure the symphsis fundus height at each study visit, plot on graph against gestational age and compare with 10th, 50th and 90th centiles and previous measurements. Any measurement <10th centile or failure to increase will be referred for an ultrasound for further fetal assessment.

Infants exposed to TDF/FTC either in-utero or during breastfeeding will have chemistry (serum creatinine) and haematological (complete blood count) at birth, 26 weeks (6 month), 50 weeks (12 months), and 72 weeks (18 months).

Infant Bone Growth:

DXA scans of the lumbar spine and whole body of infants will be performed at 6 weeks, 6 months, 12 months and 18 months to determine BMC and bone growth.

Clinical Examination of Infants:

Clinical examination of infants at birth will be conducted as per standard of care prescribed in the SA paediatric guidelines. This will include examination for physical abnormalities.

Physical examination of infants will include OFC, weight, and length to monitor growth and also include assessments for neurodevelopmental milestones at 6 weeks, 3 months, 6 months, 12 months and 18 months.

